**Table 2: Study objectives and endpoints**

Objectives	Endpoints
Primary	
To assess the safety of RUAT Echo	Adverse events Serious adverse events Adverse device effect Serious adverse device effects
To assess the useability (functionality) of using the RUAT echo as intended to obtain echocardiogram images of clinically suitable quality for reporting by a cardiac sonographer.	Verification of functional requirements Participant experience

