#### 11.1.1 Decision Criteria

The primary objectives of the study are to:

- assess the **safety** of the RUAT echo.
- assess the **“useability” (functionality)** of using the RUAT echo as intended to obtain echocardiogram images of clinically suitable quality for reporting by a cardiac sonographer.

The **safety** of the RUAT Echo will be considered acceptable if there are no device related adverse effects.

RUAT Echo will be considered a **useable** method of performing echocardiograms if:

- Each functional verification criteria 1 through 11 (inclusive) performed “YES” at least 80% of the time an echocardiogram was performed by RUAT Echo, that is, pass functional verification (see APPENDIX 1 - Functional Verification ).
- At least 80% of echocardiograms performed by RUAT Echo are considered of an adequate quality to provide a diagnostic assessment, that is, pass functional verification item #12 (see APPENDIX 1 - Functional Verification ).
- At least 80% of participants report they are satisfied with undergoing RUAT Echo examination based on an average of the 4 subscales of the 10-point Likert scales from strongly disagree to strongly agree (see APPENDIX 2 – Participant Survey).

	QMS Template	Doc ID: RMI-ROBOTECHO-CIP-002 Ver No: V2.0
	Clinical Investigation Protocol	

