### 11.3.2 Useability (functionality)

The RUAT Echo device will be deemed as being **sufficiently useable (functional)** (i.e., technically non-inferior) **if each of the 12 Functional Verification Criteria** (see APPENDIX 1 - Functional Verification ) result in "YES"  $\geq 80\%$  of the time.

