#### 11.3.2.1 Main Analytical Approach

The proportion of RUAT echocardiograms deemed to be of sufficient quality will be summarised descriptively along with a 95% confidence interval.

Participant experience will be summarised descriptively.

Adverse events and serious adverse events will be coded using the Medical Dictionary for Regulatory Affairs and will be summarised by system organ class and preferred term by echocardiogram type (conventional vs RUAT Echo). No statistical comparisons between adverse events or serious adverse events by scan type are planned.

Adverse device effects will be coded using the FDA Medical Device Report (MDR) adverse event codes and will be summarised by Level 1 Term and Level 3 Term by echocardiogram type (conventional vs RUAT Echo).

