#### 11.6 Sample Size Determination

Approximately 30 participants will be recruited. A single-group design will be used to obtain a two-sided 95% confidence interval for a single proportion of the RUAT Echo images that are deemed of sufficient quality. The Exact (Clopper-Pearson) formula will be used to calculate the confidence interval. The sample proportion is assumed to be 80%. With a sample size of 30, the width of the associated confidence interval is 30.9% around the 80% (that is, from 61.4% to 92.3%).

Confidence interval widths were computed using PASS 2023, version 23.0.2.

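### The two statements of the usability success rule agree on the 12 checklist items but differ on whether 80% participant satisfaction is required

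*Protocol*

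**What the plan says.** Table 2 lists two endpoints under the usability objective: "Verification of functional requirements Participant experience".

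Section 11.1.1 (Decision Criteria) calls RUAT Echo a useable method if three bullets are met:

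- "Each functional verification criteria 1 through 11 (inclusive) performed “YES” at least 80% of the time an echocardiogram was performed by RUAT Echo";
- "At least 80% of echocardiograms performed by RUAT Echo are considered of an adequate quality to provide a diagnostic assessment", which it identifies with checklist item 12;
- "At least 80% of participants report they are satisfied with undergoing RUAT Echo examination based on an average of the 4 subscales" of the survey.

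Section 11.3.2 then gives its own verdict. The device is deemed sufficiently useable, glossed as functional and technically non-inferior, "if each of the 12 Functional Verification Criteria" is answered YES at least 80% of the time. Satisfaction is not mentioned.

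Section 11.3.2.1, on the analysis, says: "Participant experience will be summarised descriptively". It sets no threshold and does not mention a proportion satisfied.

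**The concern.** Usability is one of only two primary objectives, and Section 18 says the report may support regulatory approval applications. A reader should be able to tell from the protocol whether that objective was met. Here the answer can depend on which section is read, because participant satisfaction is a condition of success in one place, absent in another, and purely descriptive in a third. No text says which section prevails, or that 11.3.2 covers only part of 11.1.1.

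Timing adds to this. Section 11 requires the statistical analysis plan to be final before database lock. In a single-group study, checklist and survey results may already be visible by then, so a choice between the rules made at that stage could not be shown to be independent of the data.

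**Working it through.** **1. The protocol's own figure.** Section 11.6 gives an exact (Clopper-Pearson) 95% interval for an observed 80% with n = 30. With x = 24:

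- lower limit = Beta quantile(0.025; 24, 7) = 0.6143
- upper limit = Beta quantile(0.975; 25, 6) = 0.9229
- width = 0.3085

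This matches the stated 61.4% to 92.3%, width 30.9%. The figure concerns image quality. It says nothing about satisfaction.

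**2. The rules side by side.**

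| Component | 11.1.1 | 11.3.2 |
|---|---|---|
| Items 1 to 11, each | at least 80% YES | at least 80% YES |
| Item 12 (images usable for reporting) | at least 80% | at least 80% YES |
| Participants satisfied | at least 80% | no condition |

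Eleven items plus item 12 make the 12 criteria, all at the same threshold, so the checklist parts are identical. Satisfaction is the only difference. Hence passing 11.1.1 implies passing 11.3.2. The verdicts differ exactly when the checklist passes and satisfaction falls below 80%.

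**3. An example.** Take n = 30 (Section 11.6: "Approximately 30 participants will be recruited"). The threshold is 0.80 × 30 = 24. Suppose every item is YES in at least 24 of 30 scans and 23 participants are satisfied, 23/30 = 76.7%. Section 11.3.2 is met and 11.1.1 is not.

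**4. How often this could happen.** Given that the checklist passes, and treating survey and checklist results as independent, the chance of differing verdicts is P(X ≤ 23), where X is binomial with n = 30 and true satisfaction rate p:

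P(X ≤ 23) = sum over k = 0 to 23 of C(30, k) p^k (1 − p)^(30 − k)

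| Assumed p | P(at least 24 of 30 satisfied) | P(verdicts differ, checklist passed) |
|---|---|---|
| 0.70 | 0.1595 | 0.8405 |
| 0.75 | 0.3481 | 0.6519 |
| 0.80 | 0.6070 | 0.3930 |
| 0.85 | 0.8474 | 0.1526 |
| 0.90 | 0.9742 | 0.0258 |
| 0.95 | 0.9994 | 0.0006 |

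**5. Without conditioning on the checklist.** Assume 12 independent items with a common true YES rate.

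- YES rate 0.95: all 12 pass with probability 0.9931. With p = 0.80, success under 11.1.1 is 0.9931 × 0.6070 = 0.603, and the verdicts differ with probability 0.9931 × 0.3930 = 0.390.
- YES rate 0.90: all 12 pass with probability 0.7305. With p = 0.80, the verdicts differ with probability 0.7305 × 0.3930 = 0.287.

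**6. What the documents say about p.** They give no rate. Table 1 reports that most proof-of-concept volunteers had some discomfort in the subcostal position, but with an earlier device. The same table concludes that sonographer and patient responses were positive throughout. Neither statement fixes a point on the scale above.

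**The case against.** The strongest reply is that the sections can be read together. Section 11.1.1 is headed as decision criteria and judges a method of performing echocardiograms. Section 11.3.2 sits among the supporting analyses, judges the device, and qualifies its verdict as functional and technically non-inferior. On that reading 11.3.2 is the technical component and 11.1.1 the overall decision. This is plausible, but the protocol does not say it. The synopsis, Table 2 and Section 11.1.1 attach the label useability (functionality) to the whole objective, and the heading of 11.3.2 repeats it. The wording therefore does not separate component from whole.

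It could also be said that the 11.1.1 bullets carry no explicit conjunction. A list after a conditional is naturally read as requiring all its parts, and reading it as alternatives would still not give the rule in 11.3.2.

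A third reply is that this is a descriptive pilot and both components will be reported, so a satisfaction shortfall would be visible under either label. That stands and limits the harm. It does not settle whether the objective is declared met.

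A fourth is that the statistical analysis plan can resolve it. It can add detail, but it would have to set aside one of two protocol statements, possibly after results are visible.

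Finally, the probabilities rest on assumed satisfaction rates and 30 completed surveys. That also stands. Recruitment is up to or approximately 30 and missing data are not imputed, so the threshold count may shift (with 28 surveys, 0.80 × 28 = 22.4, so 23 are needed). Any count also presumes a cut-off for satisfied, which the protocol does not state and the analysis plan may supply.

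**Conclusion.** The point holds. Sections 11.1.1, 11.3.2 and 11.3.2.1 give participant satisfaction three different roles, so the verdict on a primary objective can differ on the same data. The disagreement is confined to that one condition and runs in one direction: 11.3.2 is never the harder rule.

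Its practical size cannot be fixed from the protocol. With 30 surveys and the checklist passed, the chance of differing verdicts runs from about 84% at a true satisfaction rate of 0.70, through 65% at 0.75, 39% at 0.80, 15% at 0.85 and 2.6% at 0.90, to 0.06% at 0.95.

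A reader might infer that the sections set unrelated success rules, or that a conflicting verdict is likely. The documents support neither. The checklist parts match exactly, and no expected satisfaction rate is given; the 80% in Section 11.6 is an assumption about image quality. Nor do they show that anyone intends to pick the easier rule. They only leave that choice open.

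**What to change.** Before any results are seen, state one usability success rule, in Section 11.1.1, by one of two routes.

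- **Satisfaction is a success condition.** Keep the three-part rule. Make 11.3.2 refer to it, or label the 11.3.2 statement as the technical component only. Have 11.3.2.1 report the proportion satisfied against the 80% threshold.
- **Satisfaction is supportive.** Remove it from the 11.1.1 success rule, and state in both 11.1.1 and Table 2 that it is supportive and descriptive. Sections 11.3.2 and 11.3.2.1 then stand as written.

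Table 2 does not decide between these, since an endpoint can be reported without being a pass/fail condition. Changing 11.3.2 alone would leave 11.3.2.1 out of line under the first route.

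The cost is a short protocol amendment, which Section 21.1 sends to the ethics committee for approval before it is implemented. Procedures, sample size and data collection do not change. Under the first route, the sponsor also accepts a rule harder to meet than 11.3.2 alone: in the illustration with a 0.95 YES rate per item and 0.80 satisfaction, the chance of success is 60.3% rather than 99.3%.

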#### 11.3.2.1 Main Analytical Approach

The proportion of RUAT echocardiograms deemed to be of sufficient quality will be summarised descriptively along with a 95% confidence interval.

Participant experience will be summarised descriptively.

Adverse events and serious adverse events will be coded using the Medical Dictionary for Regulatory Affairs and will be summarised by system organ class and preferred term by echocardiogram type (conventional vs RUAT Echo). No statistical comparisons between adverse events or serious adverse events by scan type are planned.

Adverse device effects will be coded using the FDA Medical Device Report (MDR) adverse event codes and will be summarised by Level 1 Term and Level 3 Term by echocardiogram type (conventional vs RUAT Echo).

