#### 4 Schedule of Assessments

Procedure	Visit Structure		
	Screening	Day of RUAT Echo	Safety Follow-up visit /End of Study  72 hours post scan
Manual echo (prior to RUAT study) 	X		
Informed consent	X		
Review inclusion and exclusion criteria 	X		
Demographics	X		
Echocardiogram using RUAT ECHO		X	
Functional verification of RUAT ECHO		X	
Participant experience Surveys 		X	
Adverse events/Adverse device events	Continuous from informed consent signature to end of study		

 Safety Follow-up visit may be conducted by telephone call or onsite if inpatient, within 72 hours after the examination.

 As part of the selection criteria participant will have recently undergone a manually performed echocardiogram. Any bruising or soreness will be documented as part of the screening and consent, ruling ineligible if the discomfort is too severe.

 Participants must have undergone a clinical (manual) echocardiogram performed and reported as per usual clinical pathway **prior** to study entry. All clinical decisions will be made based on this echocardiogram.

 Participant survey to be completed on paper after the RUAT Echo with the support of the observing sonographer.

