### 9.1 Inclusion criteria:

- Male or female aged 18 years or older
- Inpatient or outpatient who has already received a routine (manual) echocardiogram that has been clinically reported.
- Is willing to participate.

	QMS Template	Doc ID: RMI-ROBOTECHO-CIP-002 Ver No: V2.0
	Clinical Investigation Protocol	

- Provides written informed consent.

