### 10.1 Administrative and Screening Procedures

#### 10.1.1 Screening and Recruitment

Prior to enrolment in the study, each participant will have already received a routine (manual) clinically reportable echocardiogram as an inpatient or outpatient.

Potential study participants will be selected based on inclusion and exclusion criteria, as above.

The potential study participant will be approached in person via a member of the study team (study coordinator or research staff as delegated by the principal investigator) while on the ward as an inpatient or in clinic as an outpatient. The study coordinator or research staff will provide details of the study (verbally and via the information sheet as part of the Participant Informed Consent Form 'PICF'), as outlined in Section 16.2.

At the time of informed consent potential study participants will be asked to disclose any bruising, soreness, or discomfort in the chest area that may impact safety outcomes that the RUAT study may have.

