#### 10.3.1 Definitions

The definitions applied for reporting adverse incidents for medical devices are those defined in ISO 14155:2020 Edition 3, July 2020.

Adverse Event (AE): Any undesirable clinical occurrence in a subject whether it is considered device related or not, that includes a clinical sign, symptom, or condition and/or an observation of an unintended technical performance or performance outcome of the device.

Adverse Device Event (ADE): A clinical sign, symptom or condition that is causally related to the presence of the device, or the performance of the device system.

An adverse event or an adverse device effect may be mild, moderate, or severe.

Serious Adverse Event (SAE): Any adverse medical occurrence that:

- Led to a death.
- Led to a serious deterioration in health of a patient user or other. This would include:
  - A life-threatening illness or injury.
  - A permanent impairment of body function or permanent damage to a body structure.
  - A condition requiring hospitalisation or prolongation of hospitalisation.
  - A condition requiring unnecessary medical or surgical intervention.
- Might have led to death or serious deterioration in health had suitable action or intervention not taken place. This includes:
  - Malfunction of a device such that it needs to be modified or temporarily/permanently taken out of service.
  - A factor (a deterioration in characteristics or performance) found on examination of the device.

Serious Adverse Device Event (SADE): A device-related serious adverse event.

Unanticipated Device Related Adverse Event: Any undesirable clinical occurrence in a subject considered device-related and not listed in the device technical manuals/Investigator’s Brochure.

	QMS Template	Doc ID: RMI-ROBOTECHO-CIP-002 Ver No: V2.0
	Clinical Investigation Protocol	

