### 10.3.2 Time Period and Frequency for Collecting AE, ADE, SAE and SADE Information

All AEs, ADEs, SAE and SADEs will be collected from the signing of the patient informed consent form (PICF) until 72 hours post RUAT Echo, i.e., end of the study.

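### Safety events are to be tabulated for conventional versus RUAT echo, but the manual echo lies outside the adverse event window for every participant

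*Protocol*

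**What the plan says.** Protocol Section 11.3.2.1 gives the planned safety summaries. Adverse events and serious adverse events "will be summarised by system organ class and preferred term by echocardiogram type (conventional vs RUAT Echo"). Adverse device effects "will be summarised by Level 1 Term and Level 3 Term by echocardiogram type (conventional vs RUAT Echo"). The same section says that no statistical comparison of adverse events or serious adverse events by scan type is planned.

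On collection, Section 10.3.2 says that all events "will be collected from the signing of the patient informed consent form (PICF) until 72 hours post RUAT Echo". The Schedule of Assessments in Section 4 agrees: "Continuous from informed consent signature to end of study".

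On the manual echo, footnote 3 to the Schedule says "Participants must have undergone a clinical (manual) echocardiogram performed and reported as per usual clinical pathway" before study entry. Section 10.1.1 says "Prior to enrolment in the study, each participant will have already received a routine (manual) clinically reportable echocardiogram", and the inclusion criterion in Section 9.1 reads "Inpatient or outpatient who has already received a routine (manual) echocardiogram that has been clinically reported".

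Two places provide for symptoms left by the manual echo. Footnote 2 to the Schedule has bruising or soreness documented at screening and consent, and makes a person ineligible if the discomfort is too severe. Section 10.1.1 has potential participants asked at consent about bruising, soreness or discomfort in the chest.

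**The concern.** A table with a conventional and a RUAT column implies that both scans were followed for events in the same way. Here one scan is over before collection begins, and the other has follow-up for up to 72 hours. Safety is a primary objective, and Section 11.3.2.1 holds the only safety summaries in the protocol; the sections that follow plan no sensitivity, supplementary or other analyses. Section 18 says that the study report may support regulatory applications. A reader of that report could take a nearly empty conventional column as evidence about the manual echo, or read the two columns as a comparison, although the data were never gathered to support one.

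**Working it through.** The protocol gives no figure on this point, and the check needs no formula beyond a count. The steps set the timing statements side by side.

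1. **Window opens:** at signature of the consent form (Sections 4 and 10.3.2).
2. **Window closes:** 72 hours after the RUAT echo (Section 10.3.2).
3. **Manual echo:** performed and clinically reported before study entry (Section 4 footnote 3, Sections 9.1 and 10.1.1). The Schedule marks it in the screening column, but the row label and footnotes 2 and 3 place it before the study, so this is no contradiction. No conventional scan is scheduled after consent.
4. **Count:** the manual echo falls inside the window for 0 of up to 30 participants. The RUAT echo falls inside it for everyone scanned.

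Next, what could fill the conventional column:

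| Feature | Manual echo | RUAT echo |
|---|---|---|
| Source | Disclosure at consent | Adverse event collection |
| Scope | Chest bruising, soreness, discomfort | Any adverse event |
| Time since scan | Not fixed; Section 9.1 sets no maximum interval | Up to 72 hours |
| Severe cases | Ineligible (Section 4 footnote 2) | Retained and reported |

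The rest of the plan does not supply the missing column either:

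- **Analysis set:** Section 11.2 defines the safety analysis set by exposure to the investigational device only.
- **Attribution:** Section 10.3.4 offers device-related, procedure-related or unknown. None of these identifies the earlier manual scan.
- **Device effects:** Section 10.3.1 defines an adverse device event as "A clinical sign, symptom or condition that is causally related to the presence of the device" or the performance of the device system. If the device is the RUAT, which is how Section 10.3.4 illustrates it, the conventional cell for device effects is empty by definition.

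Last, what depends on the column. Section 11.1.1 calls safety acceptable if no device-related adverse effects occur. That is an absolute criterion on the RUAT, so its result is the same whether the conventional column is filled, empty or removed.

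**The case against.** The strongest reply is that this is a pilot with descriptive summaries, that the protocol expressly disclaims a statistical comparison of adverse events by scan type, and that the safety criterion looks only at device-related effects. All of that stands. A reader might infer that the safety conclusion itself is compromised, but the documents do not support this.

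A second reply is that the soreness recorded at consent is the natural content of the conventional column. This stands in part. A reader might infer that nothing at all is recorded after the manual echo, and footnote 2 and Section 10.1.1 show otherwise. But the record is narrow, taken at an unfixed time, and cut off at the severe end by eligibility. It describes the participant's state on entering the study, so it is baseline information and does not match what the RUAT column counts.

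A third reply is that the SAP may say how events map to scan type. A reader might also infer that an event between consent and the RUAT scan must be placed under conventional. No section says so; it could equally be left unassigned. The lack of a mapping rule is a matter for the SAP and is not the error. The error is that the protocol fixes a column the design cannot fill. Section 11 says the SAP will describe these same analyses in more detail, so a SAP that follows the protocol inherits the column, and one that drops it departs from the protocol.

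**Conclusion.** The point holds as an inconsistency between the planned table and the collection window. For all of up to 30 participants the manual echo precedes the window, so a conventional column would be empty or not comparable with the RUAT column. For device effects it would be empty by definition, on the reading that the device is the RUAT.

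The consequence is a misleading descriptive table for a primary objective. The pass or fail decision on safety, the safety analysis set and the sample size are unaffected. The split should be corrected, but it does not threaten the study's conclusion.

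The conclusion rests on the manual echo always preceding consent, which the three sections cited for its timing state consistently, and on no other record of events after the manual echo being planned; the protocol describes none.

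**What to change.** In Section 11.3.2.1, delete the split by echocardiogram type from both sentences: the one on adverse and serious adverse events, and the one on adverse device effects. In its place:

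- tabulate events with onset from the start of the RUAT scan to 72 hours afterwards, in the safety analysis set;
- list events with onset between consent and the start of the scan separately;
- report bruising, soreness or discomfort disclosed at consent as a baseline finding, not as an adverse event of the conventional echo.

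The sentence disclaiming comparison by scan type then has no purpose and can go.

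The cost is a wording change and simpler tables. No new data or participants are needed, although event onset must be recorded precisely enough to place it before or after the start of the scan. The change is best made before the SAP is finalised. A genuine side-by-side description would instead need prospective event collection after the manual echo, which is a change of design.
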